13. ETHICAL AND REGULATORY PROCEDURES

13.1 Research Standards/Good Clinical Practice

This study will be conducted in accordance with all applicable guidelines for the protection of human subjects for research as outlined in 21 CFR 50 the accepted standards for Good Clinical Practice (GCP), and the standard practices of the study sites in accordance with the protocol and amendment(s) as applicable.

13.2 Quality Assurance/Audit/Inspection

To ensure compliance with GCP and all applicable regulatory requirements, Galderma Laboratories, L.P. may conduct a quality assurance audit of the site records, and the regulatory

Protocol Version 02: 29 January 2024

This document contains confidential, proprietary information.

Protocol GLI.04.US.SL.035

CONFIDENTIAL

agencies may conduct a regulatory inspection at any time during or after completion of the study. The Investigator must agree to grant the auditor(s) and inspector(s) direct access to all relevant documents and to allocate their time and the time of their staff to discuss any findings/relevant issues.

13.3 Institutional Review Board

This study (protocol, ICF and all addenda) will be reviewed and approved by Sterling IRB. The study will not be activated and subjects will not be consented, receive any study products, or participate in any study procedures until the IRB has approved the protocol and the ICF. In addition, the IRB will review the study before any significant change in the protocol is initiated. After each review, the IRB's approval will be documented in a letter to the Investigator and a copy of the IRB approval letter will be forwarded to the Sponsor.

14. STUDY CONDUCT CONSIDERATIONS

14.1 Clinical Monitoring

The conduct of the study will be closely monitored by representatives of Galderma Laboratories, L.P. following GCP, ICH guidelines, applicable SOPs, guidelines, and all local regulations. The clinical investigation will be monitored to ensure that: the rights and well-being of the subjects are protected; the reported data are accurate, complete and verifiable from applicable source documents; and the study is conducted in accordance with the currently approved protocol and any other study agreements, GCP, and all applicable regulatory requirements. The Investigator will allow the Galderma Laboratories, L.P. representatives to have access to all study records, CRF/eCRF, corresponding subject medical records, and any other documents considered source documentation. The Investigator also agrees to assist the representatives, if required, which can include AE reporting.

14.2 Study Deliverables

All study data and digital images will be forwarded to the Sponsor. Images will be labeled with study number, subject number, and timepoint.

14.3 Data Collection

Investigators must keep accurate records of all subjects' visits and all procedures done, being sure to include all pertinent study related information from which CRF/eCRF data will be recorded. Data for this study may be recorded in the subject's chart (e.g., source documents / electronic records) or if approved by the Galderma Laboratories, L.P. directly into CRF/eCRFs. If electronic records are maintained, the method of verification must be determined in advance of starting the study. The process of administering the informed consent must also be documented. Any and all side effects and AEs with the concomitant therapies associated must be thoroughly documented. Results of any diagnostic tests conducted during the study should be included in the source documentation. Pertinent telephone conversations with the subjects and/or Galderma Laboratories, L.P. concerning the study will be documented and kept on file.

Protocol GLI.04.US.SL.035

CONFIDENTIAL

It is required that the author of an entry in the source documents be identifiable. Direct access to all source documentation (medical records) must be allowed for the purpose of verifying that the data recorded in the CRF/eCRF are consistent with the original source.

Only designated individuals may complete the CRF/eCRFs. The principal Investigator will review the reported data and certify that the CRF/eCRFs are accurate and complete.

After monitoring has occurred at the clinical site(s) and the CRF/eCRFs have been reviewed, additional data clarifications and/or additions may be needed including AE reporting. Data clarifications and/or additions are documented and are part of each subject's CRF/eCRFs.

14.4 Data Management

A double-entry method will be used to enter data captured on paper records into a spreadsheet database to ensure accurate data transfer, and any missing data and/or inconsistencies will be identified and corrected.

The self-assessment questionnaire will be completed by subjects electronically using HIPAA-compliant SurveyMonkey online survey software. Paper questionnaires may be completed if needed.

All images taken from the study will be saved and shared to the Sponsor via a data-protected platform.

14.5 Record Retention

The Investigator is required to maintain up-to-date, complete regulatory documentation as indicated by Galderma Laboratories, L.P. and the Investigator's files will be reviewed as part of the ongoing study monitoring. The records must be easily accessible when needed (e.g., for a Galderma Laboratories L.P.'s audit or regulatory inspection) and must be available for review in conjunction with assessment of the facility, supporting systems, and relevant site personnel. Financial information is not subject to regulatory inspection and should be kept separately.

Galderma Laboratories, L.P. will inform the Investigator of the time period for retaining the site records in order to comply with all applicable regulatory requirements. The minimum retention time will meet the strictest standard applicable to a particular site, as dictated by local laws/regulations, Galderma Laboratories, L.P. SOPs, and/or institutional requirements.

The Investigator should take measures to prevent accidental or premature destruction of these documents. If the Investigator retires, relocates, or for other reasons withdraws from the responsibility of keeping the study records, custody must be transferred to a person who will accept the responsibility. Galderma Laboratories, L.P. must be notified in writing of the name and address of the new custodian.

14.6 Changes in Study Conduct/Amendments

No amendment will be done for modification(s) due to change in logistical or administrative aspect of the study (e.g., change in monitors, change of telephone numbers). In such a case, the appropriate institution(s) and/or person(s) will be notified of the changes.

Protocol Version 02: 29 January 2024

This document contains confidential, proprietary information.

Protocol GLI.04.US.SL.035

CONFIDENTIAL

Modification of the protocol is prohibited without prior written agreement in the form of a protocol amendment. All amendments will be created by Galderma Laboratories, L.P. and must be approved by the IRB prior to implementation except when required to mitigate immediate safety risks or when the changes involve only logistical or administrative revisions.

Amendments may necessitate that the informed consent and other study-related material be revised. If the consent form is revised, all Subjects/subjects currently enrolled in the study may be required by the IRB to sign the approved, revised informed consent form.

APPENDIX I: INGREDIENT LISTS

CETAPHIL® GENTLE SKIN CLEANSER

FORMULA NO: L2-2688A.1 (1747)

INGREDIENTS:

WATER
GLYCERIN
CETEARYL ALCOHOL
PANTHENOL
NIACINAMIDE
PANTOLACTONE
XANTHAN GUM
SODIUM COCOYL ISETHIONATE
SODIUM BENZOATE
CITRIC ACID

CETAPHIL® MOISTURIZING CREAM

FORMULA NO: L2-2299A.1 (1765)

INGREDIENTS:

WATER
GLYCERIN
PETROLATUM
DICAPRYLYL ETHER
DIMETHICONE
GLYCERYL STEARATE
CETYL ALCOHOL
HELIANTHUS ANNUUS (SUNFLOWER) SEED OIL
PEG-30 STEARATE
PANTHENOL
NIACINAMIDE
PRUNUS AMYGDALUS DULCIS (SWEET ALMOND) OIL
TOCOPHERYL ACETATE
PANTOLACTONE
DIMETHICONOL
ACRYLATES/C10-30 ALKYL ACRYLATE CROSSPOLYMER
CARBOMER
PROPYLENE GLYCOL
DISODIUM EDTA
BENZYL ALCOHOL
PHENOXYETHANOL
SODIUM HYDROXIDE
CITRIC ACID

Protocol GLI.04.US.SL.035

CONFIDENTIAL

CETAPHIL® DAILY FACIAL MOISTURIZER SPF 35

FORMULA NO: 217-19229-42 (1727)

ACTIVE INGREDIENTS:

AVOBENZONE 2.8%
HOMOSALATE 9.5%
OCTISALATE 4.8%
OCTOCRYLENE 7.0%

INACTIVE INGREDIENTS:

WATER
GLYCERIN
DIPROPYLENE GLYCOL
PANTHENOL (VITAMIN B5)
ETHYLHEXYL METHOXYCRYLENE
ISOPROPYL PALMITATE
SILICA
NIACINAMIDE
CETEARYL OLIVATE
CETEARYL ALCOHOL
GLYCERYL STEARATE
POTASSIUM CETYL PHOSPHATE
SORBITAN OLIVATE
TOCOPHERYL ACETATE (VITAMIN E ACETATE)
CAPRYLYL GLYCOL
ACRYLATES/C10-30 ALKYL ACRYLATE CROSSPOLYMER
PALMITIC ACID
ETHYLHEXYLGLYCERIN
STEARIC ACID
LEONTOPODIUM ALPINUM FLOWER/LEAF EXTRACT
1,2-HEXANEDIOL
ORYZA SATIVA (RICE) LEES EXTRACT
PROPANEDIOL
SODIUM HYDROXIDE
ADENOSINE
CITRIC ACID
MYRISTIC ACID
TOCOPHEROL (VITAMIN E)
BUDDLEJA DAVIDII (SUMMER LILAC) LEAF EXTRACT
THYMUS VULGARIS (THYME) LEAF EXTRACT

Protocol GLI.04.US.SL.035

CONFIDENTIAL

APPENDIX II: QUALITY OF LIFE QUESTIONNAIRE

DERMATOLOGY LIFE QUALITY INDEX

DLQI

Study Site:

Date:

Score:

Subject Number:

Diagnosis:

Address:

The aim of this questionnaire is to measure how much your skin problem has affected your life OVER THE LAST WEEK. Please check one box for each question.

1.	Over the last week, how itchy, sore, painful or stinging has your skin been?	Very much A lot A little Not at all	   	
2.	Over the last week, how embarrassed or self conscious have you been because of your skin?	Very much A lot A little Not at all	   	
3.	Over the last week, how much has your skin interfered with you going shopping or looking after your home or yard ?	Very much A lot A little Not at all	   	Not relevant 
4.	Over the last week, how much has your skin influenced the clothes you wear?	Very much A lot A little Not at all	   	Not relevant 
5.	Over the last week, how much has your skin affected any social or leisure activities?	Very much A lot A little Not at all	   	Not relevant 
6.	Over the last week, how much has your skin made it difficult for you to do any sport ?	Very much A lot A little Not at all	   	Not relevant 
7.	Over the last week, has your skin prevented you from working or studying ?	yes no	 	Not relevant 
	If "No", over the last week how much has your skin been a problem at work or studying ?	A lot A little Not at all	  	
8.	Over the last week, how much has your skin created problems with your partner or any of your close friends or relatives ?	Very much A lot A little Not at all	   	Not relevant 

Protocol GLI.04.US.SL.035

CONFIDENTIAL

9.	Over the last week, how much has your skin caused any sexual difficulties ?	Very much A lot A little Not at all	   	Not relevant 
10.	Over the last week, how much of a problem has the treatment for your skin been, for example by making your home messy, or by taking up time?	Very much A lot A little Not at all	   	Not relevant 

©AY Finlay, GK Khan, April 1992, This must not be copied without the permission of the authors.

Please check you have answered EVERY question. Thank you.

DERMATOLOGY LIFE QUALITY INDEX (DLQI) - INSTRUCTIONS FOR USE

The Dermatology Life Quality Index questionnaire is designed for use in adults, i.e. patients over the age of 16. It is self explanatory and can be simply handed to the patient who is asked to fill it in without the need for detailed explanation. It is usually completed in one or two minutes.

SCORING

The scoring of each question is as follows:

Very much	scored 3
A lot	scored 2
A little	scored 1
Not at all	scored 0
Not relevant	scored 0
Question 7, 'prevented work or studying'	scored 3

The DLQI is calculated by summing the score of each question resulting in a maximum of 30 and a minimum of 0. The higher the score, the more quality of life is impaired.

HOW TO INTERPRET MEANING OF DLQI SCORES

0 – 1	no effect at all on patient's life
2 – 5	small effect on patient's life
6 – 10	moderate effect on patient's life
11 – 20	very large effect on patient's life
21 – 30	extremely large effect on patient's life

REFERENCES

Finlay AY and Khan GK. Dermatology Life Quality Index (DLQI): a simple practical measure for routine clinical use. *Clin Exp Dermatol* 1994; **19**:210-216.

There is more information about the DLQI, including over 85 translations, at www.dermatology.org.uk. The DLQI is copyright but may be used without seeking permission by clinicians for routine clinical purposes. For other purposes, please contact the copyright owners.

APPENDIX III: SELF-ASSESSMENT QUESTIONNAIRE**Week 2**

	Strongly agree	Agree	Neither agree nor disagree	Disagree	Strongly disagree
The cleanser leaves my skin feeling clean					
The cleanser doesn't irritate my skin					
This cleanser doesn't dry my skin out					
My skin feels nourished after using the regimen					
It is easy to incorporate this skincare regimen into my daily prescription routine					
This moisturizer has helped the lesions feel softer					
The skin lesions feel smoother since starting this moisturizer					
My skin looks healthier since starting this moisturizer					
The moisturizer keeps my skin feeling hydrated throughout the day					

Week 4

	Strongly agree	Agree	Neither agree nor disagree	Disagree	Strongly disagree
My skin is less dry and cracked					
I worry less about my skin since starting the regimen					
These skincare products work well with my prescription treatment as a complete regimen					
This moisturizer helps smooth out my skin's rough texture					
My skin appears healthier-looking since starting this moisturizer					
The skin lesions feel much softer since starting this moisturizer					

Protocol GLI.04.US.SL.035

CONFIDENTIAL

This moisturizer has helped the lesions feel more hydrated					
The skin lesions look less flaky since starting this moisturizer					

Week 8

	Strongly agree	Agree	Neither agree nor disagree	Disagree	Strongly disagree
The cleanser is gentle for daily use on my psoriasis skin					
My skin feels the least irritated since starting this skincare regimen					
My skin hasn't felt this great in a long time					
This is my favorite skincare regimen					
This skincare regimen was the perfect choice as part of my prescription regimen					
My skin is at the healthiest-looking state since using this moisturizer					
This moisturizer helps sooth my sensitive skin					
I love how soft my skin feels					
The skin lesions have been consistently hydrated since using this moisturizer					
This moisturizer helps smoothen out the rough, scaly lesions					

	Yes	No
I would recommend the cleanser to my family and friend		
I would recommend the moisturizer to my family and friend		
I would recommend the product regimen to my family and friend		
I would purchase the cleanser		
I would purchase the moisturizer		
I would purchase the product regimen		

Protocol GLI.04.US.SL.035

CONFIDENTIAL

Testimonials (please provide any comments on your experience, study products, satisfaction/dissatisfaction, or anything related to this study)

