6.3 Inclusion Criteria

The subjects must meet all the following criteria to be eligible for the study:

1. Adult subjects aged 18 years and above
2. Females or males
3. Any Fitzpatrick skin types I-VI, with effort to include $n = 2$ for each category
4. Any races, with effort to include minimum 10% minority ($n = 4$) such as American Indian or Alaska Native, Eastern/Southeastern Asian, South Asians, Black or African American, Native Hawaiian or Other Pacific Islander.
5. Any ethnicities, with effort to include minimum 10% ($n = 4$) of Hispanic, Latino, or Spanish origin
6. Having active target lesion plaques, with minimum area of 2 cm x 2 cm
7. Having mild-to-severe plaque psoriasis with at least 3% Body Surface Area (BSA) and cumulative Target Lesion Severity Score (TLSS) ≥ 6 .
8. Currently on or starting a plaque psoriasis prescription treatment such as biologics, oral or topical therapy for psoriasis, or UV therapy.
9. Subject in general good health
10. Subject willing to stop using current topical skincare products during the duration of the study.
11. Subject willing to replace current skincare products with study products for the duration of the study.
12. For female subjects of childbearing potential, she must not be pregnant, breastfeeding or planning pregnancy during the course of the study. Subjects must be willing to take a urine pregnancy test (UPT) at Baseline visit.
 - Females of non-childbearing potential, e.g., post-menopausal (absence of menstrual bleeding for 1 year without any other medical reason), hysterectomy, or bilateral ovariectomy, are not required to have a UPT.

Protocol Version 02: 29 January 2024

This document contains confidential, proprietary information.

Protocol GLI.04.US.SL.035

CONFIDENTIAL

13. Ability of giving consent for participation in the study
14. Willing to sign a photography release, with minimum 80% of total study panel
15. Agreement to adhere to the procedures and requirements of the study and to report to the site on the day(s) and at the time(s) scheduled for the assessments.

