6.5.1. Authorized Therapies

Prescription treatments for plaque psoriasis, including biologics, oral or topical therapy for psoriasis, and UV therapy, are required for this study.

Protocol Version 02: 29 January 2024

This document contains confidential, proprietary information.

Protocol GLI.04.US.SL.035

CONFIDENTIAL

Unless listed under the exclusion criteria (see Section 6.4) or in Prohibited Therapies (see Section 6.5.2), other therapies to treat ongoing conditions are authorized.

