8.3 Subject Instructions for the Study

Subjects will be provided with the following instruction to follow during the study:

8.3.1. Study Product Usage Instructions:

The study products are used on both face and body:

- *Step 1: Cleanser* – wet skin with lukewarm water, apply the cleanser to wet skin and massage gently. Rinse well and pat dry.
- *Step 2: Moisturizer* – at least twice daily, in the morning and evening, apply the moisturizer liberally to the lesions and all over the body. Reapply the moisturizer as needed throughout the day.
 - If your psoriasis treatment is topical prescription, you can first apply the prescription treatment following its instruction. Wait at least 10 minutes before applying the study moisturizer to the lesions and all over.
- *Step 3: Sunscreen SPF 35* – if you are planning on spending time outdoors, apply the sunscreen to entire face and body before sun exposure once the moisturizers are fully absorbed.

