Questionnaires will be tabulated; and the frequency and percentage of all response options will be reported for each question and time point. For questionnaire inquiries without baseline response data, a binomial (sign) test will be performed to test if the proportion of the combined designated favorable responses is equal to the combined designated unfavorable responses for each applicable question. A higher percentage of favorable responses with a significant *p* value indicates positive subject perceptions of the study treatment.

A more appropriate analysis may be performed, which will be recorded in biostatistics note to file and/or in the study report.

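### The Week 2 item on fitting the regimen into a daily prescription routine presupposes a daily prescription and has no not-applicable option; it and the two related items are planned only pooled over all prescription types

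*Combined protocol and SAP*

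**What the plan says.** Three Appendix III items ask how the regimen fits with the prescription:

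- Week 2: "It is easy to incorporate this skincare regimen into my daily prescription routine"
- Week 4: "These skincare products work well with my prescription treatment as a complete regimen"
- Week 8: "This skincare regimen was the perfect choice as part of my prescription regimen"

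Each has five agreement options with a neutral midpoint and no not-applicable box.

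Inclusion criterion 8 (section 6.3) admits anyone "Currently on or starting a plaque psoriasis prescription treatment such as biologics, oral or topical therapy for psoriasis, or UV therapy". Section 6.5.1 adds: "Prescription treatments for plaque psoriasis, including biologics, oral or topical therapy for psoriasis, and UV therapy, are required for this study". Neither sets a treatment frequency, a quota or a stratum by type.

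Section 8.3.1 gives an extra step to one group only: "If your psoriasis treatment is topical prescription, you can first apply the prescription treatment following its instruction", followed by "Wait at least 10 minutes before applying the study moisturizer to the lesions and all over".

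Under section 12.4, "the frequency and percentage of all response options will be reported for each question and time point". Items without a baseline are also tested with a binomial (sign) test of favourable against unfavourable answers, and a significant favourable majority is read as positive perception of the study treatment. Section 12 does not mention prescription type.

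**The concern.** The Week 2 wording assumes something that eligibility does not guarantee. A subject whose prescription is not taken or applied daily has no clearly correct answer, and the plan gives no instruction. An agreement from that subject would be tabulated and tested like one from a subject who layers two products on the same lesion every day.

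The Week 4 and Week 8 items make sense for any prescription, so the word 'daily' is no problem there. What all three share is the pooling. Subjects who put a prescription product and the study cream on the same skin have a different experience of fit from those who do not, and the planned output cannot show whether the two groups agree. What is at stake is any statement that the regimen fits well with topical prescriptions.

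**Working it through.** The plan states no expected response, power or prescription mix for these items, so there is no figure to reproduce. The check is what the planned test can and cannot show.

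**Inputs from the protocol.** 40 to 50 completers (section 6.1); two-sided tests at 5% (section 12.1); sign test per question (section 12.4).

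**Assumptions.** Topical share, response rates and neutral rate. The two agreement options count as favourable and the two disagreement options as unfavourable. Neutral answers drop out of the test, which section 12.4 does not state.

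**Step 1: threshold of the pooled test.** With k favourable of n non-neutral answers and k > n/2, p = 2 × P(X ≥ k), X ~ Binomial(n, 0.5).

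- n = 40: 27 favourable gives p = 0.0385; 26 gives 0.0807.
- n = 50: 33 favourable gives p = 0.0328; 32 gives 0.0649.

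The test can thus be favourable with 40 − 27 = 13, or 50 − 33 = 17, unfavourable answers. Nothing in the plan shows whether these come mainly from topical users.

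**Step 2: an illustration (assumed answers).** Twenty topical users: 9 favourable, 9 unfavourable, 2 neutral. Twenty others: 14, 1 and 5.

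- Topical: 9 of 18, p = 1.0.
- Others: 14 of 15, p = 0.001.
- Pooled: 9 + 14 = 23 favourable and 9 + 1 = 10 unfavourable; 23 of 33, p = 0.0351.

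This sits near the threshold: 22 against 10 gives p = 0.0501, and 22 against 11 gives p = 0.080.

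**Step 3: how often, over a range of mixes.** With no neutral answers, the chance of a favourable pooled result is P(X_T + X_O ≥ k), where X_T ~ Binomial(n_T, p_T) for topical users, X_O ~ Binomial(N − n_T, p_O) for the others, and k comes from step 1. With p_O = 0.9:

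| Topical share | N = 40, p_T = 0.3 | N = 50, p_T = 0.3 | N = 40, p_T = 0.5 |
|---|---|---|---|
| 20% | 0.98 | 0.995 | 0.996 |
| 30% | 0.85 | 0.92 | 0.97 |
| 40% | 0.49 | 0.58 | 0.89 |
| 50% | 0.15 | 0.18 | 0.72 |

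Allowing neutral answers at the step 2 rates (topical 45% / 45% / 10%, others 70% / 5% / 25%), the chance at N = 40 is 0.92, 0.56, 0.19 and 0.10 at topical shares of 30, 50, 70 and 80%.

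**Step 4: the neutral option.** If all 20 non-topical subjects in step 2 chose neutral, the test would rest on the topical answers alone, 9 of 18, p = 1.0, and nothing would be masked.

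**Step 5: what a split could deliver.** At a topical share of 20 to 50%, the topical group has 8 to 20 subjects (N = 40) or 10 to 25 (N = 50). If 30% of them are truly favourable, a sign test within the group is significantly unfavourable with probability 0.06 (n = 8), 0.15 (n = 10), 0.42 (n = 20) or 0.51 (n = 25). The split can describe; it cannot confirm.

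**The case against.** Four arguments carry weight.

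- *The items are peripheral.* They are 3 of 33 closed items (9 at Week 2, 8 at Week 4, 16 at Week 8) under a secondary objective on satisfaction. A reader might infer that a pooled result would misstate the trial's main question. The documents do not support that: the primary objective concerns efficacy and tolerability, its subject-reported measures are itching and burning/stinging (section 11.1), and section 12.4 claims only positive perception. This stands and makes the point minor.
- *Non-topical answers need not be favourable.* A reader might infer that ease is trivially true for these subjects because they have nothing to combine. But everyone takes on a cleanser and an all-over cream at least twice daily, oral therapy may well be daily, and the neutral midpoint is open to all. This stands. What remains is that nobody is directed to the midpoint and its handling in the test is unstated.
- *The two groups overlap.* Section 3 says that most patients on biologics also use topical therapy. This stands, and any split must place mixed users explicitly.
- *Nothing is lost.* Data are listed by subject (section 12.1), therapies are recorded (section 6.5), and section 12.4 allows an alternative analysis. True, but a split chosen after the answers are seen is weaker than a planned one, and no later analysis can identify Week 2 answers from subjects to whom the item did not apply.

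**Conclusion.** The point holds in a limited form. The Week 2 item presupposes a daily prescription that eligibility does not require. All three items are planned only as pooled results, although section 8.3.1 itself treats topical users differently. A favourable pooled test can therefore coexist with divided answers among topical users.

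The size is not known. Under the assumed rates the chance of a favourable pooled result runs from near certainty at a 20% topical share to 0.10 at 80%, and masking disappears if non-topical subjects choose neutral. That biologic or UV subjects may lack a daily routine is an inference; the documents give no frequencies. They do not support a claim that a positive result would be driven by non-topical subjects, only that the planned output could not tell.

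The mix is further obscured because exclusion 6 (section 6.4) lists prescription corticosteroids for psoriasis, immunosuppressive agents and monoclonal antibodies, while inclusion 8 and section 6.5.1 admit or require biologic and topical therapy. These passages must be reconciled.

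**What to change.** 1. Add to the Week 2 item the option *Not applicable: I have no daily prescription*, and leave those answers out of its denominator and sign test. The study's DLQI form already offers a comparable option on eight of its ten questions.
2. State in section 12.4 that the three items will also be reported descriptively (counts, percentages, 95% confidence intervals) for subjects with any topical psoriasis prescription, including those also on biologic, oral or UV therapy, versus those with none. Use the therapies recorded under section 6.5.
3. Limit any statement about compatibility with topical prescriptions to the first group.
4. State how neutral answers enter the sign test.
5. Reconcile exclusion 6 with inclusion 8 and section 6.5.1.

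For items 1 to 4 the cost is one response option, a few sentences in section 12.4 and one table; no new data are collected. Because Appendix III is part of the protocol, the new option needs an amendment under section 14.6. The downside is small groups with wide intervals, so no confirmatory subgroup test should be planned.
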